### 7.4.4 Concomitant Medications

Medications will be coded by the WHO Drug Dictionary.

Concomitant medications are the medications taken with a start date on or after the start of the administration of study treatment (C1D1), or those with a start date before the start of the administration of study treatment (C1D1) and a stop date on or after the start of the administration of study treatment (C1D1). Medications taken beyond 30 days from the last dose of study treatment or after the start of an alternative anti-leukemia treatment are not considered concomitant medications, unless they are used for treating a related SAE.

For the purpose of determining whether a medication is a concomitant medication, incomplete medication start and stop dates will be imputed conservatively following the data programming standards as detailed in the Astex Data Programming Conventions.

Concomitant medications will be summarized by WHO Drug Dictionary Therapeutic Subgroup (ATC level 2) and Drug Name, sorted alphabetically, using counts and percentages.

Special interest concomitant medications include anti-emetic drugs, growth factors, broad-spectrum antibiotics, and antifungals. These concomitant medications will be tabulated separately. Transfusions will be described separately as part of the efficacy analyses (Section 7.3.8).

### 7.4.5 Laboratory Tests

Data from different local laboratories will be standardized to consistent SI units, and presented in data listings. Laboratory values recorded as an interval such as " $\geq x$ ", " $< x$ ", or "2+" will be handled, if necessary for calculation purposes, following the data programming standards as detailed in the Astex Data Programming Conventions.

Laboratory values will be graded, if relevant and possible, by CTCAE version 4.03 in conjunction with the Harrison (18th edition) lab book normal values (Longo et al 2011). Shift tables will display (1) shift from baseline grade to the worst grade during the study, and (2) shift from baseline grade to the last grade at the end of study.

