9.5.2 Screening and Baseline Procedures

After the investigator or sub-investigator confirms that a subject is eligible and willing to participate in the study, study center personnel will randomly assign the subject to study treatment according to the study procedures manual.

Within 14 days before randomization (unless otherwise specified), perform the following study procedures and tests:

- Written informed consent. The ICF must be signed and dated by the subjects before any study-specific samples are collected or study-specific procedures are initiated.
- Complete medical history, including demographics. Record disease history, including the date of initial diagnosis and list prior treatments and responses to these treatments. Document concurrent medical signs and symptoms to establish baseline conditions. Prior treatments for MDS or other hematologic disorder, CMML, and AML should be recorded.
- Investigator's confirmation of eligibility. Perform all necessary procedures and evaluations to document that the subject meets each eligibility criterion.
- Complete physical examination including weight and examination of body systems according to institutional standards.
- Vital signs include resting systolic/diastolic blood pressure, resting respiration rate, resting heart rate, and body temperature.
- ECOG performance status.
- Height measurement (for BSA calculation).
- All study-procedure-related AEs from the time of informed consent.
- Record concomitant medications within 14 days before randomization.
- Blood and urine sample collection for laboratory assessments. (See [Table 17](#))
- Serum or urine pregnancy test: for women of child-bearing potential only, collected within 7 days before starting study treatment. Results must be negative for the subject to be eligible for enrollment into the study.
- Blood sample collection for cytogenetics and molecular genetics, collected within 28 days before starting study treatment.
- BM aspirate or biopsy for baseline disease assessment, cytogenetics, and molecular genetics, collected within 28 days before starting study treatment.
- All blood and platelet transfusions (blood product transfused and units) within 28 days before starting study treatment.
- Study treatment randomization, after eligibility is confirmed. Randomize as close as possible to the first dose of study treatment (on Cycle 1 Day 1), within a maximum of 1 week from Cycle 1 Day 1.

Table 17: Clinical Laboratory Tests

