9.5.6 Long-term Follow-Up

Long-term follow-up starts after subjects discontinue study treatment. Long-term follow-up visits will be either monthly or every 3 months, depending on when the subject discontinues study treatment:

- For subjects who discontinue treatment before Cycle 6, initial follow-up visits will be conducted monthly (± 7 days) until 6 months after the start of study treatment, and then visits will be conducted every 3 months (± 2 weeks), until death.
- For subjects who discontinue treatment after Cycle 6, long-term follow-up visits are required every 3 months (± 2 weeks), until death.

Monthly long-term follow-up procedures (for subjects who discontinue treatment before Cycle 6):

- Health-related QOL EQ-5D-5L ([Appendix 4](#)).
- Hospital admission and discharge dates (and the main reason for hospitalization), as well as all blood and platelet transfusions (blood product transfused and units), since the last visit.
- Subsequent anti-leukemia therapy (regimen and start date).
- For subjects with no documented disease progression on treatment:
 - Hematology and/or BM aspirate/biopsy (≥ 1 year after the start of study treatment, BM aspirate/biopsy every 6 months) until disease progression or relapse is documented.
 - Disease progression status.
- Survival follow-up.

Long-term follow-up procedures for visits every 3 months (± 2 weeks) (for subjects who discontinue treatment after Cycle 6 and for subjects have completed the monthly long-term follow-up visits described above):

- Subsequent anti-leukemia therapy (regimen and start date).
- For subjects with no documented disease progression:
 - Hematology and/or BM aspirate/biopsy (≥ 1 year after the start of study treatment, BM aspirate/biopsy every 6 months).
 - Disease progression status.
- Survival follow-up.

Long-term follow-up visits may be conducted by telephone if needed.

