## 7.2 Demographic and Other Baseline Characteristics

The demographic variables consist of age, age category, sex, ethnicity, race and geographical region. Baseline characteristics include height, weight, body surface area (BSA), ECOG performance status, AML category by French-American-British (FAB) classification as well as by WHO classification, time since AML diagnosis, whether the AML is secondary to MDS or other antecedent hematologic disorder, cytogenetic risk levels, peripheral blood counts of hemoglobin, platelets, total white blood cells (WBCs) with blasts counts, BM blasts and presence of baseline genetic mutations in several genes including but not limited to FLT3-ITD, NPM1, and CEBPA. Other baseline variables such as relevant medical history or other medically relevant criteria could also be included in the baseline tables.

Baseline values are generally the values collected right before randomization during the screening period. For analysis purposes, the value collected closest to but before randomization will be used as the baseline value for a particular variable. For variables which are collected on Day 1 of Cycle 1 (C1D1) but not during the screening period, the C1D1 values will be used as the baseline values.

Age at baseline, if not already provided through data collection, will be calculated as the integer part of  $(\text{date of consent} - \text{date of birth})/365.25$ .

Time since diagnosis will be calculated as the  $(\text{date of randomization} - \text{date of diagnosis})$ . If the day is missing for date of diagnosis, the 15th of the month is used. If the month is missing, July 1st is used. If the year is missing, the date is left as missing. Additional date imputation details are contained in the Astex Data Programming Conventions.

Subject demographic and baseline characteristics will be summarized by mean, standard deviation, median, minimum, and maximum for continuous variables; and by counts and percentages for categorical variables. Both the Efficacy and Safety Analysis Sets will be used for the summaries.

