## 7.4 Safety Variables and Analyses

All safety analyses will be performed using the Safety Analysis Set which includes data from all subjects who receive any amount of study treatment (guadecitabine or TC; see [Section 5.3](#)).

Safety is assessed by subject-reported and investigator-observed AEs, and 30-day and 60 day all-cause mortality, along with concomitant medications, physical examination, clinical laboratory tests (hematology, serum chemistry, and urinalysis), vital signs, ECOG performance status, and ECGs. Safety is also assessed by exposure to guadecitabine or TC, reasons for discontinuation, deaths and causes of deaths.

All safety data collected during the study will be included in the study database. All safety data collected during the study will be used for generation of safety summary tables, with the exception of AEs and medications. The AE and medication summary tables will only include treatment-emergent AEs and concomitant medications as defined in [Sections 7.4.2 and 7.4.4](#).

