## 7.4.2 Adverse Events

AE terms reported by study subjects or observed by investigators will be mapped to the appropriate System Organ Class (SOC) and Preferred Term (PT) according to the Medical Dictionary for Regulatory Activities (MedDRA). Severity of AE will be graded using Common Terminology Criteria for Adverse Events (CTCAE) version 4.03.

Treatment-emergent AEs are defined as events that first occurred or worsened after the first dose of study drug given on C1D1 until 30 days after the last dose of study treatment or the start of an alternative anti-leukemia treatment, whichever occurs first, with the following exceptions: events that occurred after 30 days beyond the last dose of study treatment or the start of an alternative anti-leukemia treatment will also be considered treatment-emergent if the events are both serious and related to the study treatment. For the purpose of determining whether an AE is a treatment-emergent AE, incomplete AE start and stop dates will be imputed conservatively following the data programming standards as detailed in the Astex Data Programming Conventions.

All AE data collected in the study database will be listed, including those that are not treatment emergent. However, safety tables will be generated based only on Treatment-emergent AEs.

An overall safety summary table containing counts and percentages of subjects with any AE, any AE Grade  $\geq 3$ , AE leading to treatment discontinuation, any serious AE (SAE), SAE leading to death, and other subjects with an SAE will be produced by treatment group. A similar table with related AE counts will also be produced by treatment group. Related events are those that the investigator considered to be suspected to be related to study treatment as described in the study protocol.

The number and percentage of subjects experiencing AEs will be summarized by MedDRA SOCs (sorted alphabetically) with PTs sorted alphabetically within each SOC, and by CTCAE grade. The number and percentage of subjects experiencing AEs will also be summarized by PT and sorted by event frequency. Related AEs, serious AEs, and related serious AEs will be summarized similarly. In summarizing AEs, if a subject reports the occurrence of a particular AE more than once, the event is only counted once with its worst CTCAE grade.

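### Laboratory shift tables use a pre-randomization baseline and have no on-treatment cut-off, so pre-dose and off-treatment values enter them

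*SAP*

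**What the plan says.** **End of the window.** SAP 7.4.5 grades laboratory values by CTCAE and shows the "shift from baseline grade to the worst grade during the study, and (2) shift from baseline grade to the last grade at the end of" the trial. SAP 7.4 gives the inclusion rule: "All safety data collected during the study will be used for generation of safety summary tables, with the exception of AEs and medications". Adverse events, by contrast, are treatment-emergent from first dose "until 30 days after the last dose of study treatment or the start of an alternative anti-leukemia treatment, whichever occurs first" (SAP 7.4.2), apart from related serious events. SAP 7.4.4 sets a similar end for medications. Protocol 11.7 describes the same shift tables and gives no window.

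**Start of the window.** Under SAP 7.2, "the value collected closest to but before randomization will be used as the baseline value for a particular variable". The one exception is: "For variables which are collected on Day 1 of Cycle 1 (C1D1) but not during the screening period, the C1D1 values will be used" as baseline. Protocol 9.5.2 reads "Within 14 days before randomization (unless otherwise specified), perform the following study procedures and tests", and its list includes "Blood and urine sample collection for laboratory assessments". Protocol 6.1 allows up to one week from randomization to treatment. Protocol 9.5.3.1 asks for hematology and chemistry before dosing on Cycle 1 Day 1 unless they were done in the preceding four days.

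**Off-treatment collection.** For subjects with no documented progression, Protocol 9.5.6 schedules "Hematology and/or BM aspirate/biopsy (≥ 1 year after the start of study treatment, BM aspirate/biopsy every 6 months"). Visits are monthly up to six months from treatment start for those who stop before Cycle 6, and three-monthly otherwise. SAP 5.3 assigns safety data to the treatment actually received.

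**The concern.** A laboratory shift table in a safety section is read as a picture of what happened to counts and chemistry while subjects were on drug. Here both ends of the window extend beyond that period. At the start, a change in counts before any study drug is given can register as a shift. At the end, values taken months after the last dose, some possibly after a transplant or another regimen, can set the worst or the last grade.

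This matters because severe or prolonged myelosuppression is a named risk (Protocol 8.0) and the trial is open-label. A laboratory finding becomes an adverse event only if judged clinically significant (Protocol 10.1.1), so graded counts are the measure of myelosuppression that depends least on unblinded judgment. As planned, they cover a different period from the adverse-event tables beside them. Off-treatment sampling also continues only while a subject has no documented progression. Treatment may affect that, so the two arms may contribute different amounts of off-treatment data.

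**Working it through.** The plan states no figure on this point, so there is none to reproduce. The check sets the rules side by side and then counts days.

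**1. Does the Cycle 1 Day 1 exception apply to laboratory values?** It covers only variables not collected in screening. Hematology and chemistry are collected in screening (Protocol 9.5.2). The exception does not apply, and the pre-randomization value is the baseline.

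**2. How old can the baseline be at first dose?** Screening window 14 days (Protocol 9.5.2) plus randomization to treatment 7 days (Protocol 6.1): 14 + 7 = 21 days at most. Any sample between randomization and first dose is not baseline, and SAP 7.4 does not exclude it, so it can count as post-baseline. Hydroxyurea and leukapheresis are allowed before randomization and prohibited after it (Protocol 7.5.1.3), so counts can move in this gap without study drug.

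**3. Is there an end date for laboratory values?** SAP 7.4 excepts adverse events and medications only. Neither SAP 7.4.5 nor Protocol 11.7 adds a limit. Starting another therapy does not stop follow-up hematology under Protocol 9.5.6; documented progression does.

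**4. How many scheduled visits can fall beyond the adverse-event cut-off?** Assumptions: 28-day cycles, last dose on Day 5 of the last cycle, 30-day months, subject alive at Day 360, no documented progression, no other anti-leukemia therapy before the cut-off, and hematology chosen at each visit. Visits fall on Days 30, 60, ..., 180, then 270 and 360. With c the last cycle given, last dose = 28 × (c − 1) + 5 and cut-off = last dose + 30.

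| Stops after cycle | Last dose | Cut-off | Visits beyond the cut-off | Count |
|---|---|---|---|---|
| 1 | Day 5 | Day 35 | 60, 90, 120, 150, 180, 270, 360 | 7 |
| 2 | Day 33 | Day 63 | 90, 120, 150, 180, 270, 360 | 6 |
| 4 | Day 89 | Day 119 | 120, 150, 180, 270, 360 | 5 |

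If the last dose falls on Day 7 or Day 10 of the cycle (the azacitidine and cytarabine schedules), the cut-off after Cycle 4 is 84 + 7 + 30 = Day 121 or 84 + 10 + 30 = Day 124. The Day 120 visit then falls inside, and the count is 4. The counts after Cycles 1 and 2 do not change.

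**5. Which way does this push the tables?** A transplant or a later regimen can worsen the worst grade. Recovery off drug can improve the last grade. A drop in counts before first dose can add a shift. The documents do not say how often any of these occurs.

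**The case against.** The strongest case against is that little of this reaches the tables, and that nothing depends on them.

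- *Descriptive tables.* A reader might infer that off-treatment cytopenias are being counted as toxicity of the study drug. The documents do not support that. Shift tables carry no attribution, relatedness is assessed for adverse events (Protocol 10.2.2), and the adverse-event tables already have a window. This stands.
- *Later chemotherapy is mostly outside scheduled collection.* SAP 7.3.3 says that other therapies are usually given at progression, and SAP 7.3.6 treats a continued blast increase that necessitates alternative therapy as progression. Scheduled hematology then stops. What remains is transplant in controlled disease (which SAP 7.3.3 foresees), a change of therapy without documented progression, and a safety visit that falls after new therapy begins. This stands.
- *Mainly hematology.* Chemistry is not scheduled after the safety follow-up visit. Follow-up visits allow hematology or marrow and may be by telephone, so the counts above are upper figures for scheduled samples. This stands.
- *The pre-dose part is small.* The 21 days are a maximum, and a pre-dose value sets the worst grade only if no later value is worse, although counts are taken on Days 8, 15 and 22 of Cycles 1 and 2. This stands in part. An outdated baseline also puts the subject in the wrong row: Grade 2 at screening, Grade 3 before dosing and Grade 3 at worst on treatment shows as a shift from 2 to 3, although nothing changed on drug.
- *QTc.* A reader might extend the point to the QTc shift table. The protocol's screening list has no ECG, so under SAP 7.2 the Cycle 1 Day 1 value is already the baseline, and no ECG is scheduled in long-term follow-up. No change is needed there.

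None of these supplies the missing window for laboratory values.

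**Conclusion.** The point holds as a defect in a stated rule. Followed as written, SAP 7.2, 7.4 and 7.4.5 put pre-dose values and off-treatment hematology into the laboratory shift tables under the treatment received. Baseline can precede first dose by up to 21 days. Under the assumptions above, 4 to 7 scheduled follow-up visits to Day 360 fall outside the adverse-event window for a subject who stops after Cycle 1, 2 or 4. These are visits at which a value may be taken, not a measure of bias. The bias can run either way, and the documents do not let its size be computed. No efficacy endpoint, alpha or decision rule is affected.

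A reader might infer that guadecitabine is 1.5 times as exposed to the problem, because the planned complete response rates give 0.30 × 400 = 120 subjects against 0.20 × 400 = 80. The documents do not support that. Those are planned responders, not subjects sampled off treatment. Guadecitabine continues while the subject benefits (Protocol 7.1.2), so responders are expected to stay on drug. The count thresholds for complete response in SAP Table 1 also make off-drug values in sustained response more likely to improve the last grade than to set the worst one.

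**What to change.** For the laboratory shift tables in SAP 7.4.5:

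1. Define baseline as the last value before the first dose of study treatment, as a stated exception to SAP 7.2.
2. In the main tables, count as post-baseline only values after first dose and within the SAP 7.4.2 window, which closes 30 days past the last dose or when another anti-leukemia treatment begins, if that is sooner.
3. Show later values in listings or in a supportive all-data table.
4. Amend the SAP 7.4 sentence on safety data so that laboratory shift tables are also excepted.

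The safety follow-up visit has a 7-day allowance beyond 30 days (Protocol 9.5.5), so the SAP should say whether samples taken in that allowance belong to the main or the supportive table.

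The cost is SAP wording, a date filter in programming and one extra table or listing. No new data are needed. The downside is that late off-treatment cytopenias leave the main table, which is why the supportive display should be kept.

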#### 7.4.6 Vital Signs

Vital signs will be summarized by visit using the proportion of subjects who have vital sign values too high or too low, according to the conventionally accepted vital sign normal ranges as listed below:

- Pulse rate  $\geq 110$  bpm.
- Pulse rate  $\leq 50$  bpm.
- Diastolic blood pressure  $\geq 110$  mmHg.
- Diastolic blood pressure  $\leq 55$  mmHg.
- Systolic blood pressure  $\geq 180$  mmHg.
- Systolic blood pressure  $\leq 80$  mmHg.
- Respiration rate  $\geq 20$  breaths/min.
- Body temperature  $\geq 39^{\circ}\text{C}$ .

#### 7.4.7 Electrocardiogram

At each ECG assessment time point (pre- and post-dose on Day 1 of Cycle 1 and on termination visit), the mean of the available electrocardiogram values (repeated three times) will be calculated and used in data listings and summary tables as the actual value for that assessment.

The following data listings will be provided to assist the medical assessment of the ECG outcomes:

- All laboratory electrocardiogram values, including the calculated mean value of each triplicate at each time point.
- All subjects who had a QTc  $>500$  ms or  $>60$  ms increase from baseline including the associated baseline values.

QTc values will also be graded based on CTCAE, and the shift table showing the shift from baseline grade to the worse grade, and from baseline grade to the last grade will be provided.

#### 7.4.8 ECOG Performance Status

ECOG performance status will be summarized by visit, at all scheduled visits where performance status was assessed, using counts and percentages.

#### 7.4.9 Physical Examination

Physical examination data will be presented in a data listing.

## 7.5 Pharmacokinetics Analysis

PK parameters will be derived using noncompartmental analyses for each subject for whom sparse PK samples were collected and successfully analyzed (PK Analysis Set; see Section 5.4). Descriptive statistics will include mean, standard deviation, minimum, median, and maximum for guadecitabine and decitabine PK parameters.

The relationship between [REDACTED] will be assessed based on the PK data and efficacy/safety data collected in this study. The methods will include a population PK modeling approach using the sparse data collected. The details of population PK modeling and full results of the [REDACTED] analyses will be reported in a separate document, and the summary of key findings will be included in the clinical study report.

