9.3 Pharmacokinetics

PK parameters will be assessed using population PK analysis. At selected study centers, sparse PK samples will be collected within windows at the time points specified below (with time of sampling recorded).

For subjects who receive SGI-110, blood sample collection will be assigned to the following time points:

- Cycle 1, Day 1, at 1.5 hours (± 30 minutes) and 3 hours (± 1 hour) postdose.
(1.5-hours sample is intended to be time-matched with the on-treatment ECG evaluation.)

AND

- Cycle 1, Day 5, at 1 hour (± 30 minutes) and 5 hours (± 2 hours) postdose.

For subjects in the TC group receiving decitabine IV, blood sample collection will be assigned to one of the following time points:

- Cycle 1, Day 1, at 30 minutes (± 10 minutes) into the IV infusion, and then immediately before the end of infusion (at 1 hour).

OR

- Cycle 1, Day 5, immediately before the end of infusion (at 1 hour); and at 5 minutes (± 2 minutes) and 3 hours (± 1 hour) after the end of infusion.

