11.8 Pharmacokinetic Analyses

PK parameters will be derived using noncompartmental analyses for each subject for whom sparse PK samples were collected and successfully analyzed. Descriptive statistics will include mean, standard deviation, minimum, median, and maximum for SGI-110 and decitabine PK parameters.

The relationship between [REDACTED] will be assessed based on the PK data and efficacy/safety data collected in this study. The methods will include a population PK modeling approach using the sparse data collected. The details of population PK modeling and full results of the [REDACTED] analyses will be reported in a separate document, and the summary of key findings will be included in the clinical study report.

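### Protocol 11.8 and SAP 7.5 prescribe individual noncompartmental PK parameters from a sparse schedule that cannot support individual AUC or half-life, while protocol 9.3 assigns those parameters to population PK (minor; descriptive PK output only)

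*SAP*

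**What the plan says.** Two methods are named for the same quantities.

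- Protocol 9.3: "PK parameters will be assessed using population PK analysis". It does not mention noncompartmental analysis.
- SAP 7.5: "PK parameters will be derived using noncompartmental analyses for each subject for whom sparse PK samples were collected and successfully analyzed".
- Protocol 11.8: "PK parameters will be derived using noncompartmental analyses for each subject", with the same continuation about sparse samples as SAP 7.5. Both sections then plan mean, SD, minimum, median and maximum of the resulting SGI-110 and decitabine parameters.
- A second paragraph, also common to protocol 11.8 and SAP 7.5, covers a partly redacted relationship with the efficacy and safety data. There, "The methods will include a population PK modeling approach using the sparse data collected".

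Protocol 9.3 sets the sampling. For SGI-110 it is "Cycle 1, Day 1, at 1.5 hours (± 30 minutes) and 3 hours (± 1 hour) postdose" and also "Cycle 1, Day 5, at 1 hour (± 30 minutes) and 5 hours (± 2 hours) postdose". For IV decitabine a subject is assigned to one of two options. The Day 1 option has one sample at 30 minutes into the infusion and one just before its end at 1 hour. The Day 5 option has one just before the end of infusion, one 5 minutes after it and one 3 hours after it.

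Neither document names the noncompartmental parameters, the trapezoidal rule, a minimum number of points, or a way to combine Day 1 with Day 5. The amendment summary (Appendix 5, item 7) says that two SGI-110 time points were added to support population PK modelling of exposure-response.

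**The concern.** A noncompartmental AUC is only as good as the sampling grid, because it joins the observed points and uses nothing else. With two points in a day the result depends heavily on when blood was drawn, and the permitted windows are wide: for SGI-110, 1-2 h and 2-4 h on Day 1, and 0.5-1.5 h and 3-7 h on Day 5. A terminal slope is normally fitted to at least three points, so half-life, extrapolated AUC and clearance are out of reach within either SGI-110 day. They are also out of reach for the decitabine Day 1 option, which has no post-infusion sample at all.

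The rationale for SGI-110 rests partly on decitabine exposure relative to IV decitabine (protocol 2.1 and 2.2.1, Table 11). A table of noncompartmental means would set the two groups side by side on different grids, and a reader could take a sampling difference for a difference in exposure. It could also disagree with the population PK report from the same samples.

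**Working it through.** **Sample count.** SGI-110: 2 (Day 1) + 2 (Day 5) = 4, which matches the total of 4 in Appendix 5. IV decitabine: 2 (Day 1) or 3 (Day 5).

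**Decitabine formed from SGI-110: assumptions.** The readable text gives no half-life, so this is an illustration. Assume a one-compartment curve with first-order input, zero predose concentration and unit scale:

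C(t) = [ka/(ka − ke)] × (e^(−ke·t) − e^(−ka·t)), with true AUC = 1/ke.

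The curve is scaled to the 60 mg/m² row of Table 11: AUC/Cmax = 89.2/27.4 = 3.26 h, treating AUC_last as total AUC. The ratio ka/ke runs from 1 to 8. Solving for ke gives 0.835 per h (true AUC 1.198) at ratio 1, and 0.413 per h (true AUC 2.419) at ratio 8.

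**Linear trapezoid at nominal times.**

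- Day 1, ratio 1: C(1.5) = 0.358, C(3) = 0.205. AUC = ½(1.5)(0.358) + ½(1.5)(0.358 + 0.205) = 0.691; 0.691/1.198 = 58%.
- Day 1, ratio 8: C(1.5) = 0.607, C(3) = 0.331. AUC = 0.455 + 0.704 = 1.159; 1.159/2.419 = 48%.
- Day 5, ratio 1: C(1) = 0.362, C(5) = 0.064. AUC = 0.181 + ½(4)(0.362 + 0.064) = 1.033; 1.033/1.198 = 86%. Over all ratios the range is 86-88%.

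**Across the permitted windows, all ratios.** Day 1 runs from 21% to 76%. The low end has both samples at 2 h, where the two windows meet: at ratio 8, C(2) = 0.499, AUC = ½(2)(0.499) = 0.499, and 0.499/2.419 = 21%. Day 5 runs from 48% to 116%. Its low end, samples at 1.5 and 3 h, is the same grid as nominal Day 1.

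**Observed Cmax, same curves.** At nominal times the larger sample is 82-97% of true Cmax on Day 1 and 96-100% on Day 5. Within the windows a single day can do worse: in the 2 h case above, 0.499 against a true peak of 0.743 is 67%.

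**IV decitabine, 1-hour infusion, assumed half-life 0.25-1 h.** With unit rate, C(t) = (1 − e^(−kt))/k up to 1 h and exponential decline after it. True AUC = 1/k.

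- Day 1 option, half-life 0.25 h: C(0.5) = 0.271, C(1) = 0.338. AUC = 0.068 + 0.152 = 0.220; 0.220/0.361 = 61%.
- Day 1 option, half-life 1 h: C(0.5) = 0.423, C(1) = 0.721. AUC = 0.106 + 0.286 = 0.392; 0.392/1.443 = 27%.
- Day 5 option, half-life 0.25 h: 0.338 at the end of infusion, 0.268 five minutes later, about 0 at 3 h after. AUC = 0.169 + 0.025 + 0.391 = 0.586; 0.586/0.361 = 162%.
- Day 5 option, half-life 1 h: 0.361 + 0.058 + 1.125 = 1.544; 1.544/1.443 = 107%.

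| Group and day | Nominal-time AUC recovered |
|---|---|
| SGI-110, Day 1 | 48-58% |
| SGI-110, Day 5 | 86-88% |
| IV decitabine, Day 1 option | 27-61% |
| IV decitabine, Day 5 option | 107-162% |

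**The case against.** A reader might infer that the SAP departs from the protocol. It does not: SAP 7.5 repeats protocol 11.8, and both also plan population PK. The inconsistency is protocol 9.3 against protocol 11.8 and SAP 7.5.

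A reader might also infer that every subject has two samples a day, or that the samples say nothing useful about exposure. Neither follows. The decitabine Day 5 option has three samples. The peak of an IV infusion falls at its end, which both decitabine options sample. Observed Cmax for SGI-110-derived decitabine is close to the truth at nominal times, and labelled concentrations remain reportable.

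The stronger defence is that the text never says AUC or half-life, nor that each day stands alone. Pooling Day 1 and Day 5 (nominal 1, 1.5, 3 and 5 h, assuming the same profile on both days) recovers 77-88% of AUC on the curves above. That is better, but it still falls short, needs a rule the plan does not contain, and does nothing for the decitabine Day 1 option.

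The overshoot for the decitabine Day 5 option also depends on the linear rule. With a log-linear rule on the falling limb, the same points give (0.169 + 0.122)/0.361 = 81% at a half-life of 0.25 h and (0.361 + 0.911)/1.443 = 88% at 1 h. The gap to the Day 1 option remains. The plan names neither rule.

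Finally, Table 11 supplies a ratio of two means with large SDs (27.4 ± 21.5 and 89.2 ± 52.9) for one analyte. Nothing here sizes the error for parent SGI-110.

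**Conclusion.** The point holds for AUC and half-life. Individual noncompartmental analysis on this schedule cannot give a terminal slope, half-life or total AUC for SGI-110 within a day, or for the decitabine Day 1 option. Protocol 9.3 assigns the same parameters to a different method, the one the added samples were meant for. This is a method the data cannot support, and not just a missing detail.

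The sample counts and the textual conflict come straight from the documents. The percentages rest on the assumed curve shapes, the assumed IV half-lives and the linear rule; they show direction and rough size, not expected results.

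Severity is minor. No PK variable is among the listed primary or secondary endpoints, the noncompartmental output is descriptive, and no hypothesis test, alpha level or sample size depends on it. A reader might infer a threat to the efficacy conclusions or to the planned analysis against efficacy and safety data. The documents do not support that, since the latter includes population PK modelling in its methods.

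**What to change.** In protocol 11.8 and SAP 7.5, replace the noncompartmental sentence so that both agree with protocol 9.3. Summarise observed concentrations by analyte, day and nominal time window, with actual sampling times listed. Take individual AUC and Cmax from the population PK model already planned, and apply the descriptive statistics to those.

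The change is to wording only, with no new samples and no new model. Its one real cost is timing: individual exposures become available only with the population PK report, so the clinical study report would carry concentrations and the summary of key findings until then.
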